1.1. Equine xenograft

The xenograft used in this study was the Gen-Os® by OsteoBiol; as described by the manufacturer, it is a carbonated nanocrystal bone mineral and collagen of natural heterologous origin, obtained by the treatment of cortical bone tissue of equine origins. Its granulometry ranges between 0.25 to 1 mm and it is described as being slightly radiopaque.

1.2. Cortical lamina

The soft lamina (OsteoBiol®) used is a 35x35mm medium curved membrane of porcine origins. Its clinical indications as described by the manufacturer: a co-adjuvant for the reconstruction or the partial or complete recovery of lost bone portions, fillers of non-infected, non-sclerotic and well blood bedewed bone defects.

1.3. Fixation

The fixation system used was the Pro-fix™ Precision Fixation System, consisting of self-drilling membrane fixation screws of 1.5 mm x 3.0 mm.

2. Study design

Fourteen patients (1 male, 13 females) aged between 27 and 64 years old were selected from the Department of Periodontology of the Faculty of Dentistry, XXXXXX

2.1. Inclusion criteria

Confining with the inclusion criteria, all the selected patients were systematically healthy, had good oral hygiene (FMPS and FMBS <20%). When presenting for implant placement and upon examination, the ridges had deficiencies in width (<4 mm, Cawood and Howell class IV) which did not allow correct implant placement. Therefore, horizontal bone augmentation procedures were proposed. All areas needing GBR, maxilla or mandible, posteriorly or anteriorly were included in this study.

2.2. Exclusion criteria

Exclusion criteria were the following: pregnant and lactating women, patients suffering from a systematic disease, patients on bisphosphonates, smokers (>10 cigarettes/day) and patients needing vertical augmentations.

Patients were given a thorough description of the procedure with a highlight on the risks, after which they received a consent form to sign before any procedure.

Ethical approval for this study was obtained from the Scientific Research Commission (USJ- 2017- 107).

2.3. Pre-surgical preparations

Clinical and radiographic examinations were done prior to any procedure. The concerned edentulous area was examined to identify the availability of keratinised mucosa and the possibility of implant placement in the mesio-distal and inter-arch planes. Radiographic examination was completed using a cone beam computed tomography (CBCT) scan of the concerned region, where the indication for

vertical augmentation was selected and excluded from the study. All the patients were given oral hygiene instructions and prophylaxis.

Each patient received 2g of Amoxicillin one hour prior to surgery. Patients were instructed to mouthrinse with chlorhexidine 0.12% gluconate mouthwash for 1 minute. Extra-oral disinfection was made using topical chlorhexidine.

2.4. *Surgical procedure*

Local and/or regional anaesthesia was obtained using Septanest® (Articaine hydrochloride 4% with adrenaline 1:100,000), depending on the concerned area.

A mid-crestal incision using a 15C blade (Swann-Morton®) was performed and extended into the sulcus of the adjacent teeth, if present. At least one vertical releasing incision extending beyond the muco-gingival junction was made. A muco-periosteal flap of full thickness was raised and extended buccally, whereas palatally it was reflected to expose 3 mm of bone and lingually the flap was elevated until reaching the mylo-hyoid line, using the Buser and the Prichard periosteal elevators (Hu-Friedy®, USA). A Rhodes back action (Hu-Friedy®, USA) was used to debride the concerned crest from any fibers and connective tissue debris (Fig. 10).

Decortication was performed using a twist drill with a stop of 3mm of length (Meisinger® 203S) to ensure a good perfusion of the grafted site (Fig. 11).

[figure not shown]

Figure 1: Incision line (a) and flap elevation (b).

[figure not shown]

Figure 2: Measuring the area to be grafted (a) and decortication (b).

Figure 3: Twist drill used for decortication (a) and the cortical lamina soaked in saline water (b).

The soft cortical lamina had been soaked in saline sterile water since the start of the surgery in order to achieve a good elasticity and easier manipulation (Fig. 12). It was then trimmed with sterile scissors and adapted to the recipient site while making sure it was not in contact with the surrounding teeth. The cortical lamina was first fixed on the palatal side (Fig. 13). The cortico-cancellous heterologous bone mix (Gen-Os®, Osteobiol) which was previously hydrated in sterile saline for 10 minutes, was placed on the ridge in sufficient quantities and covered by the membrane while being adapted in the desired shape of the future ridge. The membrane was reclined and also fixated on the buccal side for better adaptability and immobilisation. Bone particles were added from the lateral sides when necessary to insure a good volume under the membrane (Fig. 14a).

[figure not shown]

Figure 4: Membrane fixated (a) and reflected (b) palatally.

Figure 5: Membrane fixated buccally (a) and horizontal mattress and single interrupted sutures (b).

In order to ensure a tension free closure, the buccal flap was advanced using a periosteal releasing incision connecting the vertical incisions thus achieving elasticity of the flap. It was followed by the brushing technique when the elasticity was not sufficient. Precaution was taken to identify and carefully isolate the mental foramen from the surrounding tissues when present. The lingual flaps were advanced using a blunt instrument (e.g. Prichard) that would detach the muscular insertion of the mylo-hyoid from the lingual flap.

Once proper elasticity was achieved, horizontal mattress sutures were placed at 4mm from the incision line using a non-resorbable PTFE 4/0 monofilament suture (Cytoplast™).

They were followed by single interrupted sutures close to the edges of the flap in order to create a connective tissue-connective tissue contact, thus creating a barrier to reduce the incidence of membrane exposure (Fig. 14b)

The vertical incisions were also closed with interrupted resorbable sutures (Novosyn® 5/0).

All patients were instructed to receive an injection of betamethasone dipropionate and disodium phosphate (Diprofos Injection- 2mL ampoule) directly after the surgery and received 2g of Amoxicillin per day for a total of 7 days.

Post-operative recommendations were clearly written and given to the patient. Chlorhexidine was prescribed starting the second day after surgery until suture removal.

Sutures were removed at 14 days, they were left for another 7 days when found necessary to secure the healing.

Patients were told not to wear their prosthesis when present for a month at least, after that the prostheses were relined with a soft liner and were worn only occasionally.

Healing was uneventful in all cases except two where an exposure occurred along with suppuration. They were treated with an extended dose of Amoxicillin (2 weeks) and with chlorhexidine rinsing. In both cases the membrane was not removed and re-epithelialization occurred after seven to ten days.

2.5. *Implant placement*

[figure not shown]
At 6 months from the surgery, a CBCT scan of the grafted area was taken and measures were made for the choice of the implant diameter and length. In all of the post-operative CBCTs, implant placement seemed possible.

On the day of the implant placement, local anaesthesia was made, followed by a mid-crestal incision and occasionally a vertical one, allowing access to the fixation screws for their removal.

The crest was debrided from any soft tissue remnants and a biopsy was taken at the site of implant placement using a trephine burr of outer diameter of 3.5mm and inner diameter of 2.5mm (Meisinger®). The trephine and bone were immersed in 10% buffered formaldehyde and fixated for histology. The implants (Straumann®, Bone Level Cylindrical) were placed at the corresponding sites of the biopsies, and the choice of a cover or a healing screw was made depending on the clinical situation and the primary stability of the implant. In most of the cases, a 2 mm of bone structure was established buccally while positioning the implant.

Implant insertion torques were noted as indicated on the implant torque wrench.

Periapical radiographs were taken, the flap was sutured and the patients received a daily dose of 2g of Amoxicillin for 7 days and diclofenac potassium (Cataflam® 50mg) inflammatory for pain management. They were also notified to mouth rinse with Chlorhexidine 0.12% for 10 days.

a

b

Figure 6: View of the crest after biopsy (a) and implant placement in the mandible (b).

3. Radiological protocol

3.1. Image acquisition

At consultation and six months after the regeneration procedure, patients were scanned with the Newtom VGI CBCT machine. Imaging conditions were: 110 kv tube voltage; 2.2 to 8.30 mA tube current; 15 x 15 cm field of view; and 0.3mm voxel size. Projection data were collected with a device rotating 360 degrees around patients over a total acquisition time of 18 seconds.

3.2. Evaluation of images

Scan data were saved in DICOM (Digital Imaging and Communications in Medicine) format and image analysis and measurements were performed using the Blue Sky Plan® (Blue Sky Bio, LLC, Grayslake, IL, USA) which provided axial, coronal and sagittal views through multiplanar reconstructions of 0.3mm slices. Axial images were reoriented to occlusal plane when present or to palatal plane as a horizontal reference. A panoramic curve was created and cross-sectional images perpendicular to that curve were reconstructed at a 1 mm interval.

3.3. Advanced jaw segmentation

For each scan, an advanced jaw segmentation technique was realized using the Blue Sky Plan software by means of threshold segmentation and contour interpolation. First the region of interest (corresponding jaw) was selected on the panoramic view. Second, several axial, coronal and cross-sectional slices equally

distributed/chosen by the software were used to draw the outline of the bone. This created a matrix to the final automatic segmentation step by the software to finalize the segmentation data and create a 3D model of the jaw. Finally, the outline of the 3D model was checked and adjusted manually on the 2D slices in all the planes in cases of over or missing contour. The result was an accurate 3D model of the corresponding jaw.

3.4. Virtual implant placement and jaw superimposition

On the post-operative CBCT plan, virtual implants were placed in the optimal position regarding bone and prosthetic reference when present.

In order to compare directly the pre and post-operative models, the pre-operative bone model was loaded into the post-operative plan and n-point registration technique was used for the superimposition of the two models. The outline of each model was visible in a unique color for comparison.

A vestibulo-lingual implant centric section perpendicular to the panoramic curve and parallel to the long axis of the simulated implant was used to make all the measurements as follow:

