3.4.1. Horizontal bone width measurements

For each implant site, pre and post-operative horizontal bone width were measured at 4 levels. Bone width was calculated from the distance between the most buccal and most lingual bone points at each level while being parallel to the simulated implant platform.

- H0-T1 and H0-T2: Pre and post-operative horizontal bone width at implant platform level.
- H2-T1 and H2-T2: Pre and post-operative horizontal bone width at 2mm apically to implant platform.
- H4-T1 and H4-T2: Pre and post-operative horizontal bone width at 4mm apically to implant platform.

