3.4.2. Vertical bone gain/loss measurements

For each implant site, pre and post-operative vertical bone gain were measured at 3 levels. Vertical bone gain/loss was calculated from the distance between the most coronal pre-operative bone points.

[figure not shown]

Figure 7: Bone superimposition and measurements at the site of implant placement.

4. Histology

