**A clinical, radiographic and histological prospective study**

Statistical Analysis Plan

Date: March 8, 2019

The statistical package software for social sciences (SPSS for Windows, Chicago, IL, USA, version 25.0) was performed for statistical analysis of the data. The alpha error was set at -p-value<0.05. Frequency and percentage were utilized to describe categorical variables. Mean and standard-deviation were used for continuous variables.

- Repeated measure analysis of variance with two within-subjects factors (Time: Baseline and six months; distance: 0mm, 2mm, 4mm, and 6 mm) was performed to compare the mean bone level within groups. It was followed by univariate analyses and Bonferroni post hoc tests.
- Repeated measure analysis of variance with one within-subjects factor (distance: 0mm, 2mm, 4mm, and 6 mm) followed by Bonferroni post hoc tests was used to compare the mean horizontal gain.
- Repeated measure analysis of variance with one within-subjects factor (level: buccal, median, lingual) followed by Bonferroni post hoc tests was executed to compare the mean vertical gain.
- One sample t tests were used to compare the mean vertical gain with a theoretical value “0” that supposed the absence of gain.
- Student t tests were performed to compare continuous variables between two groups.
- Pearson correlation coefficients were calculated to assess the relationship between continuous variables.

Kruskal-Wallis tests were used to compare histomorphometric measurements between different levels.

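### Does the plan need a rule for the pre-operative width at 0 mm when that level, set on the post-operative scan, lies above the old crest?

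*Protocol*

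**What the plan says.** Protocol section 3.4 places the reference implant on the six-month scan: "On the post-operative CBCT plan, virtual implants were placed in the optimal position regarding bone and prosthetic reference when present". The pre-operative model is then registered to that plan, so one section, axis and platform serve both time points. Section 3.4.1 defines the top level as "H0-T1 and H0-T2: Pre and post-operative horizontal bone width at implant platform level" and the measure itself as follows: "Bone width was calculated from the distance between the most buccal and most lingual bone points at each level". Section 3.4.2 adds a height measure: "For each implant site, pre and post-operative vertical bone gain were measured at 3 levels".

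The SAP uses the 0 mm level twice. The first analysis is "Repeated measure analysis of variance with two within-subjects factors (Time: Baseline and six months; distance: 0mm, 2mm, 4mm, and 6 mm"), and the second, on horizontal gain, is "Repeated measure analysis of variance with one within-subjects factor (distance: 0mm, 2mm, 4mm, and 6 mm) followed by Bonferroni post hoc tests". It also tests height change: "One sample t tests were used to compare the mean vertical gain with a theoretical value" of zero.

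Sections 2.2 and 2.3 of the Protocol exclude patients who need vertical augmentation, with the CBCT used to identify them. Neither document gives the depth of the virtual platform relative to either crest, or a rule for a level at which one model has no bone.

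**The concern.** A width needs a buccal and a lingual bone point. If the graft has raised the crest and the platform sits above the old one, the pre-operative model has neither point at 0 mm. The exclusion of vertical cases makes this less likely but not impossible: the graft is laid on the ridge and shaped, and the plan measures and tests height change.

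Two entries are then possible, and they give different analyses. A zero puts some height gain into the horizontal gain at 0 mm, so a difference between 0 mm and the deeper levels could partly show where the platform was put. A blank removes the site at every level from a standard repeated-measures ANOVA. The two planned ANOVAs cannot check each other: with two time points, the time-by-distance interaction and the distance effect on gain are the same F test. A reader who is not told the rule could misread a 0 mm effect.

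**Working it through.** The plan states no figure on this point, so there is nothing to reproduce. What can be checked is how much the unwritten rule could matter.

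**Inputs.** From the documents: 14 patients (Protocol section 2), four distances and alpha 0.05 (SAP), entry ridge width below 4 mm (Protocol section 2.1). Assumed: one site per patient; pre-operative crest width w of 1–3 mm; k affected sites.

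**1. Entering zero.** The mean 0 mm gain rises by k × w / 14 compared with a case in which those sites kept a pre-operative width w.
- k = 1: 1/14 to 3/14 = 0.07–0.21 mm
- k = 2: 0.14–0.43 mm
- k = 3: 0.21–0.64 mm

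Example with an assumed post-operative width of 6 mm and w = 3 mm: leaving affected sites out gives a mean gain of 3.00 mm. Entering zero gives (13 × 3 + 1 × 6)/14 = 3.21 mm for k = 1 and (12 × 3 + 2 × 6)/14 = 3.43 mm for k = 2. The overall time effect averages four distances, so even k = 3 with w = 3 mm moves it by only 0.64/4 = 0.16 mm.

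**2. Leaving a blank.** Error df = 3(n − 1): 39 at n = 14, 33 at n = 12, 30 at n = 11. A distance effect with 80% power at n = 14 (noncentral F) has 72% at n = 12 and 67% at n = 11. Entering zero avoids this loss.

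**3. The distance test with zeros entered.** Simulation: 20,000 trials per setting, 14 sites, equal true gain at all four levels, SD 1.0–1.5 mm, between-level correlation 0.3–0.6, w added at 0 mm in k sites. Any rejection counts as an error here, which treats the added height as artefact.

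| Affected sites | Sphericity assumed | Greenhouse-Geisser | Any Bonferroni contrast with 0 mm |
|---|---|---|---|
| 0 | about 5% | about 4% | 2–3% |
| 1 | 4–5% | 3–4% | 1–2% |
| 2 | 5–12% | 4–7% | 2–3% |
| 3 | 6–30% | 5–18% | 3–6% |

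The 30% arises only with a 3 mm crest, the smaller SD, the higher correlation and no correction.

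**4. Would dropping 0 mm give a clean check?** With the artefact at 0 mm alone, a test on 2, 4 and 6 mm rejects in 4–5% of trials, but that result is built in. A platform above the old crest also moves the 2 mm level coronally, onto a narrower part of a tapering ridge. If half the artefact is assumed at 2 mm, the reduced test with sphericity assumed rejects in up to 8% (k = 2) or 14% (k = 3).

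**5. How often?** Expected number = 14 × P(vertical change > platform depth below the post-operative crest), with a normal change. Mean 0, SD 0.5 mm, depth 1 mm: 14 × 0.023 = 0.3 sites. Mean 1 mm, SD 0.5 mm, depth 0: 14 × 0.977 = 13.7 sites. Plausible assumptions give almost none to almost all, so the documents cannot settle it.

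**The case for a change.** The best case for a change is that the gap in the text is certain and closing it is cheap. Comparing gain across levels is a named SAP analysis, the 0 mm level carries any height change, and neither the entry rule nor the count of affected sites can be recovered from the plan. Nor is the count bounded at three, the most that was simulated. With more affected sites, an overall distance test could largely reflect platform position.

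What stands is that a results table should say how many sites had no pre-operative bone at 0 mm. What does not follow is that the planned analysis is wrong. Zero is the true width at a level with no bone, and the post-operative width minus zero is the bone gained at the platform, which is what section 3.4.1 defines. It is an artefact only for a reader who takes the 0 mm gain to mean widening of existing ridge.

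The larger remedies gain little. The run without 0 mm is not shown to be clean. Measuring again from the pre-operative crest needs reader time and a judged ridge axis, and could itself favour narrow baseline sections. It would be set against a frame with a clear merit: both models are read on one section, at the place where the implant is planned.

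**Conclusion.** No change to the plan follows. This is a missing detail that analysts fill sensibly: a level without bone has width 0, and entering it so loses no site. The cost is 0.07–0.21 mm on the mean 0 mm gain per affected site. One affected site brings no inflation of the distance test. Two bring at most about 7% with Greenhouse-Geisser, or 12% without. Three bring up to 18% or 30% in the least favourable setting, while the Bonferroni contrasts needed for a claim about 0 mm stay at 3–6%.

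These figures assume 14 independent sites, a 1–3 mm crest, equal true gain at all levels and height gain counted as artefact. They do not cover more than three affected sites. The frequency cannot be established from the documents: platform depth is not given, vertical cases are excluded, and the figure of the measurements is not shown in the text reviewed. The overall before/after comparison is not in doubt. One sentence in the results with the number of affected sites, and the mean 0 mm gain with and without them, would tell the reader all that is needed.

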3.4.1. Horizontal bone width measurements

For each implant site, pre and post-operative horizontal bone width were measured at 4 levels. Bone width was calculated from the distance between the most buccal and most lingual bone points at each level while being parallel to the simulated implant platform.

- H0-T1 and H0-T2: Pre and post-operative horizontal bone width at implant platform level.
- H2-T1 and H2-T2: Pre and post-operative horizontal bone width at 2mm apically to implant platform.
- H4-T1 and H4-T2: Pre and post-operative horizontal bone width at 4mm apically to implant platform.

3.4.2. Vertical bone gain/loss measurements

For each implant site, pre and post-operative vertical bone gain were measured at 3 levels. Vertical bone gain/loss was calculated from the distance between the most coronal pre-operative bone points.

[figure not shown]

Figure 7: Bone superimposition and measurements at the site of implant placement.

4. Histology

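### Does leaving the position of the three vertical readings unstated (Protocol 3.4.2) undermine the vertical-gain analysis?

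*Protocol*

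**What the plan says.** Protocol 3.4.2 states that, for each implant site, "pre and post-operative vertical bone gain were measured at 3 levels", and then that "Vertical bone gain/loss was calculated from the distance between the most coronal pre-operative bone points". It does not name the levels, locate them or give a direction. Figure 7 belongs to this section, and its caption says that it shows the superimposition and the measurements; the image is not in the text reviewed.

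Protocol 3.4 sets the frame. The pre-operative model is superimposed on the post-operative one, and "A vestibulo-lingual implant centric section perpendicular to the panoramic curve and parallel to the long axis of the simulated implant was used" for every measurement. Protocol 3.4.1 places the horizontal widths in millimetres from the implant platform and parallel to it. Protocol 3.2 adds an earlier step: "Axial images were reoriented to occlusal plane when present or to palatal plane as a horizontal reference".

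The SAP names the vertical levels buccal, median and lingual. It compares them by repeated-measures ANOVA and tests mean vertical gain against 0 with one-sample t tests.

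**The concern.** Taken literally, a distance between pre-operative points contains no change over time. Once that is read as a slip, position is still open, and two readings can be defended:

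- **On the ridge:** the buccal, middle and lingual parts of the old crest, which the reference to the most coronal pre-operative points suggests.
- **At the implant:** the buccal edge, centre and lingual edge of the simulated implant, which the implant-centred section suggests.

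They need not agree in these patients. At inclusion, "upon examination, the ridges had deficiencies in width (<4 mm", so the buccal edge of an implant may lie outside the old crest. A line there starts on the old buccal wall, and added width is then counted as added height. The exclusion criteria rule out "patients needing vertical augmentations", so a reader may take the test against 0 as asking whether crest height was kept. With implant-edge lines, an unchanged crest could show a significant buccal gain and a difference between levels, both produced by width.

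**Working it through.** The documents give no vertical value, standard deviation or implant diameter, so there is no figure of the plan's own to reproduce. The check has two parts.

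**1. How far apart can the readings be?**

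Inputs from the documents: pre-operative width under 4 mm (Protocol 2.1); "a trephine burr of outer diameter of 3.5mm and inner diameter of 2.5mm" for the biopsy at the implant site (Protocol 2.5); "15 x 15 cm field of view; and 0.3mm voxel size" (Protocol 3.1).

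Assumptions: flat old crest of width w0; vertical, unchanged lingual wall; buccal wall widening s mm per mm of depth; new crest at the same height, widened buccally; implant diameter 3.5 mm, equal to the outer diameter of the trephine; lingual bone of thickness l.

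- The buccal implant edge lies l + 3.5 mm from the lingual wall. With l of at least 0.5 mm that is at least 4.0 mm, outside any crest under 4 mm.
- Ridge reading: 0 mm at all three levels, because the crest has not moved.
- Implant reading, buccal: max(0, (l + 3.5 − w0)/s). With l = 1 and w0 = 3 this is 1.5/s, which gives 1.5, 3.0 and 6.0 mm for s = 1.0, 0.5 and 0.25.
- Extremes: (0.5 + 3.5 − 3.9)/1.0 = 0.1 mm and (1.5 + 3.5 − 2)/0.25 = 12 mm.
- Implant reading, median: max(0, (l + 1.75 − w0)/s), from 0 to (1.5 + 1.75 − 2)/0.25 = 5.0 mm.

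A second sketch used rounded crests, an assumed 4.1 mm implant, and assumed widths of 2 to 3.9 mm before and 6 to 8 mm after surgery. Differences from a crest-to-crest reading were:

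| Reading | Difference (mm) |
|---|---|
| Line at buccal implant edge, symmetric graft | 1.3 to 7.4 |
| Line at buccal implant edge, buccal graft | 3.4 to 13.9 (no reading within 15 mm in 21 of 81 settings) |
| Each model's own buccal shoulder | −0.40 to −0.14 |
| Line inside the old crest | −0.74 to +0.26 |

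Only the implant-edge line departs by millimetres, and its smallest value in the first sketch (0.1 mm) is below one 0.3 mm voxel.

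For scale, if the t test uses 14 independent values, it is significant once the mean exceeds t(0.975, 13)/√14 = 0.58 standard deviations, or 0.58 mm for an assumed SD of 1 mm. A millimetre shift could therefore change the result. The number of implant sites is not given.

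**2. What does the text leave open?**

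- *Pre to post, with a sign.* The section covers gain and loss, the two models are overlaid, and the SAP tests the mean against 0. Only a signed change fits all three. The missing post-operative point is a slip of wording.
- *Direction.* The section used for every measurement runs parallel to the implant axis, and horizontal means parallel to the platform. Vertical along the implant axis is the counterpart. The reorientation in 3.2 comes before the panoramic curve is drawn and sets no measuring axis inside the section. Direction does not move the ridge reading in the first sketch: any line through a point of a flat, unchanged crest meets the new surface at that same point, so the value is 0 at every tilt.
- *Position.* This is open in the surviving text, and Figure 7 is the natural place for it to be shown.

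**The case for a change.** The strongest case for a change is that narrow ridges are exactly where the two readings part, that the SAP runs inferential tests on the result, and that stating landmarks, axis and sign would take two or three sentences. Without them, a reader of the text alone cannot say whether a buccal gain means height or width.

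Part of this stands. The text is thinner here than in 3.4.1, and if the recorded lines are at the implant edges, the buccal result is bone change at that edge and should be described that way. That is a matter of reporting.

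The rest does not carry. The missing position may come only from the missing figure. The millimetre gap depends on a wall slope, a lingual thickness and an implant diameter that the documents do not give; simulating the tests would only return the slope put in. Requiring crest-anchored lines would replace one defensible measure with another. Bone at the implant edge is a reasonable quantity in a protocol that centres every section on the implant, and the documents nowhere say that crest height is the target.

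**Conclusion.** No change to the plan follows. The sentence in 3.4.2 contains a clerical omission (no post-operative point) and leaves position to the figure or to the person measuring. The intended quantity, its sign, the section and the natural axis can all be recovered from 3.4, 3.4.1 and the SAP.

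The possible size is real but conditional: 1.5 to 6.0 mm at the buccal level in the central example and 0.1 to 12 mm over all the settings of the straight-walled sketch, and then only if the lines are at the implant edge, the buccal wall slopes as assumed and the result is read as crest height. Other plausible pairs differ by less than 1 mm. The documents do not show which reading was used, and no stated rule is wrong under either. The conclusion rests on treating Figure 7 as part of the plan although it could not be seen. If it does not mark the lines, the gap in description remains, but the planned tests can still be run as written.
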